7.2 Primary Analysis

The timing for the primary analyses of PFS for arm 1 vs arm 2 will be event driven and will happen when approximately 188 PFS events are reached cumulatively.

CCI

CCI

Testing of the key secondary endpoints will be performed using a fixed sequence hierarchical testing procedure in the order of ORR, MRD[-]CR, and OS such that the overall Type I error rate is strongly controlled under 0.025 (1-sided). PFS, ORR, MRD[-]CR and OS will be tested at the PFS primary analysis.

The hierarchical testing procedure will be applied as following:

- PFS (arm 1 vs arm 2) is tested at alpha level of 0.025 at the primary analysis
- If PFS is significant at the primary analysis, then ORR, MRD[-]CR are tested sequentially at alpha level of 0.025. Starting with the hypothesis of ORR, if any hypothesis in the sequence is rejected at a 1-sided significance level of 0.025, then the subsequent hypothesis will be tested. Otherwise, if any hypothesis failed to be rejected, then the subsequent hypotheses will not be tested.
- If PFS, ORR, and MRD[-]CR are all statistically significant, then OS will be tested multiple times with an overall alpha of 0.025. During the primary analysis, OS will be tested at a significance level of 0.001 per [section 7.1](#).

CCI

8. Data Screening and Acceptance

8.1 General Principles

The objective of the data screening is to assess the quantity, quality, and statistical characteristics of the data relative to the requirements of the planned analyses.

8.2 Data Handling and Electronic Transfer of Data

The Amgen Global Study Operations-Data Management (GSO-DM) department will provide all data to be used in the planned analyses. This study will use the RAVE database. Laboratory data will be collected by COVANCE Central Laboratory Services and transferred to Amgen GSO-DM periodically in cumulative files. Quality of life data

will be collected by ERT and transferred to Amgen GSO-DM periodically in cumulative files.

8.3 Handling of Missing and Incomplete Data

The descriptive statistics will identify the extent of missing data. Rules for handling missing data related to endpoints are described in the endpoint definitions or in the description of analyses. The handling of incomplete and partial dates for adverse events and concomitant medications are described in [Appendix A](#).

8.4 Detection of Bias

If applicable the methods to detect bias are described in the analyses of particular endpoints.

8.5 Outliers

Pharmacokinetic (PK) concentration data will be evaluated for outliers by visual inspection, and decisions to re-assay individual samples will be made in accordance with standard pharmacokinetic evaluation practice.

8.6 Distributional Characteristics

If applicable the distributional characteristics will be explored for particular endpoints.

8.7 Validation of Statistical Analyses

Programs will be developed and maintained, and output will be verified in accordance with current risk-based quality control procedures.

Tables, figures, and listings will be produced with validated standard macro programs where standard macros can produce the specified outputs.

The production environment for statistical analyses consists of Amgen-supported versions of statistical analysis software; for example, the SAS System version 9.4 or later.

9. Statistical Methods of Analysis

9.1 General Considerations

The efficacy analyses of PFS and key secondary endpoints will be conducted on the full analysis set. Treatment effects in efficacy endpoints will be evaluated and compared between KdD vs Kd.

In principle, summary statistics including mean, standard deviation, median, first and third quartiles, will be provided for continuous variables. Frequency and percentage will be summarized by treatment arm for binary and categorical variables. Proportions and

the corresponding 95% CI will be based on **Clopper-Pearson Method** and the treatment comparison will be based on Cochran-Mantel-Haenszel test. Exact tests will be considered for subgroup analyses when the cell size is considered small. Time to event endpoints will be estimated using the Kaplan-Meier (K-M) method. Stratified log-rank test statistics and associated p-values will also be calculated. Hazard ratios will be estimated using stratified Cox proportional hazards models. **Stratification factors include original International Staging System (ISS) stage (Stage 1 or 2 vs Stage 3) at screening; prior proteasome inhibitor exposure (yes vs no); number of prior lines of therapy (1 vs ≥ 2); prior cluster differentiation antigen 38 (CD38) antibody therapy (yes vs no). A stratification factor will not be used if any level of the factor contains less than 5% of the whole population.**

The adequacy of the proportional hazard assumption will be assessed using the plot of the logarithm of the estimated hazard function based on the Kaplan-Meier method against the logarithm of time-to-event endpoints. The scaled Schoenfeld residuals by time plot will be examined for evidence of a non-zero correlation, which indicates non-proportionality. In addition, a treatment-by-time(log) interaction test will be performed using a Cox model with stratification factors.

For PFS, response and disease progression will be determined by an IRC in a blinded manner. In addition, response and disease progression outcomes will be determined locally by investigators in an unblinded manner and centrally by the sponsor using a validated computer algorithm (Onyx Response Computer Algorithm, ORCA) in a blinded manner. The primary analysis of PFS will be based on IRC assessed outcomes; the timing will be event driven and will happen when approximately 188 PFS events are reached. The PFS outcomes assessed by the investigators as well as by ORCA will serve as supportive analyses of PFS.

The primary comparison of PFS will be tested using a log rank test stratified by the randomization stratification factors per IxRS at 1-sided significance level of 0.025.

9.2 Subject Accountability

The number and percent of subjects who were screened, randomized, received study treatment, entered long-term follow-up before disease progression and long-term follow up for survival will be summarized by treatment group. The number and percent of subjects who discontinued study treatment, long-term follow-up before disease progression, and study will be tabulated, along with the reason for discontinuation. The number and percent of subjects randomized will be tabulated by the stratification factors.

The number and percent of subjects randomized will be tabulated by study site. Key study dates for the first subject randomized, last subject randomized, and data cut-off date for analysis will be presented.

9.3 Important Protocol Deviations

Important Protocol Deviations (IPDs) categories are defined by the study team before the first subject's initial visit and updated during the IPD reviews throughout the study prior to database lock. These definitions of IPD categories, subcategory codes, and descriptions will be used during the course of the study.

9.4 Demographic and Baseline Characteristics

Demographic and baseline disease characteristics will be summarized by treatment group and overall using descriptive statistics for the Full Analysis Set. These include, but are not limited to the following.

- Baseline demographics and characteristics:
 - Age at randomization
 - As continuous variable
 - As categorical variable: <75, ≥ 75 years
 - **As categorical variable: 18 – 64, 65 – 74, 75 – 84, ≥ 85 years**
 - Sex (Male, Female)
 - Race (White and other categories depending on frequency observed)
 - Ethnicity (Hispanic or Latino, Not Hispanic or Latino)
 - **Height (cm)**
 - Weight (kg)
 - Body surface area (m²) (**as continuous in m²; as categorical variable: ≤ 2.2, > 2.2 m²**)
 - Body mass index
 - Region (North America, Europe, Asia **Pacific**, Other)
 - Frailty status (**Fit, Intermediate Fitness, Frail, Not available**)
- Baseline organ function and comorbid conditions:
 - ECOG performance status (0-1 [0, 1], 2)
 - Hemoglobin (g/L) (**as continuous in g/L; as categorical variable: < 105, ≥ 105 g/L**)
 - Absolute Neutrophil Count (**10⁹/L**) (**as continuous in 10⁹/L; as categorical variable: < 1.5, ≥ 1.5 *10⁹/L**)
 - Platelet count (10⁹/L) (**as continuous in 10⁹/L; as categorical variable: < 105, ≥ 105 *10⁹/L**)

- Corrected calcium (mg/dL): calculated **by Covance (central laboratory)** as [serum calcium (mg/dL) + 0.8×(4 - serum albumin (g/dL))] **(as continuous in mg/dL; as categorical variable: ≤11.5, > 11.5 mg/dL)**
- Creatinine clearance (CrCl, **as continuous in mL/min; as categorical variable: < 15, 15 - < 30, 30-<50, 50-<80, ≥80 mL/min**): Measured or calculated CrCl according to the Cockcroft-Gault formula **by Covance (central laboratory)**:

$$CrCL(mL / min) = \frac{(140 - Age) \times Weight(kg)}{72 \times S_{Cr}(mg / dL)} \times (0.85 \text{ female})$$

- **Left ventricular ejection fraction (LVEF) (%)**
- **Baseline ECG (Normal, Abnormal and not clinically significant, Abnormal and clinically significant, not evaluable)**
- Baseline hypertension history (yes/no)
- Baseline history of ischemic heart disease (yes/no)
- Baseline disease characteristics:
 - **Original ISS stage per IXRS at screening (I or II, III)**
 - **Original ISS stage at baseline (I, II, III)**
 - Revised ISS stage at baseline (I, II, III)
 - MM subtype (**IgG, IgA, IgD, IgE, IgM, None; Kappa, Lambda, Not detectable within each subtype**)
 - Determination of measurable disease at baseline (**based on SPEP only, based on UPEP only or both SPEP and UPEP, based on SFLC only**)
 - β 2-microglobulin level (**as continuous in mg/L; as categorical variable: < 3.5, ≥ 3.5 and < 5.5, ≥ 5.5 mg/L**)
 - **Albumin (as continuous in g/dL; as categorical variable: < 3.5, ≥ 3.5 g/dL)**
 - **SFLC Kappa/Lambda ratio (Normal, Abnormal)**
 - Presence of plasmacytoma (yes, no)
 - **Presence of bone lesion (Yes, No)**
 - **Plasma cell involvement in bone marrow (%) (as continuous in %; as categorical variable < 50%, ≥ 50%)**
 - Risk group as determined by **genetic abnormality per IMWG** (high-risk group, standard-risk group, **and unknown group**)
 - Time from Initial Multiple myeloma diagnosis to randomization (months)
 - Number of prior lines of therapy (**as continuous variable and as categorical variable 0, 1, 2, 3, and > 3**)
 - Prior Lenalidomide exposure (yes, no)
 - Refractory to Lenalidomide exposure (yes, no)
 - Prior Bortezomib exposure (yes, no)
 - **Refractory to Bortezomib exposure (yes, no)**
 - **Prior Bortezomib or Ixazomib exposure (yes, no)**

- **Refractory to Bortezomib or Ixazomib exposure (yes, no)**
- Prior Proteasome Inhibitor exposure (yes, no)
- **Refractory to Proteasome Inhibitor exposure (yes, no)**
- **Prior IMiD exposure (yes, no)**
- **Refractory to IMiD exposure (yes, no)**
- **Best overall response to last prior systemic therapy (sCR, CR, VGPR, PR, SD, PD)**
- Refractory to the last prior line of therapy (yes, no)
- Prior Transplant (yes (Autologous, Allogeneic), no)
- **Number of prior transplant (1, 2, > 2)**

9.5 Efficacy Analyses

The efficacy analyses will be based on the Full Analysis Set.

Table 3. Efficacy Endpoint Summary Table

Endpoint	Primary Summary and Analysis Method	Sensitivity Analysis
Primary Endpoint		
Progression-Free Survival	Based on IRC assessments: 
 • KM summaries • 1-sided p-value from stratified log-rank test. Hazard ratio and 95% CI from stratified Cox regression.	
 • Investigator assessments: same as primary summary and analysis method based on investigator assessments. • Internal computational assessments: Same as primary summary and analysis method based on ORCA assessments. • Unstratified analyses: 1-sided p-value from unstratified log-rank test, hazard ratio and 95% CI from unstratified Cox regression. • Initiation of new anti-myeloma therapy treated as PFS Event: The data censoring rules are the same as those for the primary analysis of PFS except that the use of new anti-myeloma therapy will be treated as an event rather than a mechanism for censoring. The same analysis method as for primary analysis will be used. • Initiation of new anti-myeloma therapy treated as neither a PFS event nor a censoring event: The data censoring rules are the same as those for the primary analysis of PFS except that the initiation of new anti-cancer therapy will be excluded as a mechanism for censoring. The same analysis method as for primary analysis will be used.

Table 3. Efficacy Endpoint Summary Table

Endpoint	Primary Summary and Analysis Method	Sensitivity Analysis
Primary Endpoint (Continued)		

MRD[-]CR (as assessed by NGS at a 10 ⁻⁵ level)	CR component based on IRC assessments: 
 Point estimate of MRD[-]CR and 95% CI by treatment group using the Clopper Pearson method. 1-sided p-value from the Cochran-Mantel-Haenszel chi-square test controlling for the randomization stratification factors per IXRS. An estimate of the common odds ratio (95% CI) will be provided as a measure of the relative treatment effect 	
 Investigator assessments: same as primary summary and analysis method based on investigator assessments. Internal computational assessments: same as primary summary and analysis method based on ORCA assessments. MRD evaluable population: same as primary summary and analysis method for MRD evaluable population. This analysis might be performed only if the MRD evaluable population is less than 90% of the ITT population.
Overall Survival	
 KM summaries 1-sided p-value from stratified log-rank test. Hazard ratio and 95% CI from stratified Cox regression. 	
 Unstratified analyses: 1-sided p-value from unstratified log-rank test, hazard ratio and 95% CI from unstratified Cox regression. Per-Protocol subset: same as primary summary and analysis method for Per-Protocol subset. This analysis might be performed only if the per-protocol population is less than 90% of the ITT population.

9.5.1 Analyses of Primary Efficacy Endpoint(s)

The distribution of PFS time including median and quartiles will be summarized descriptively using the Kaplan-Meier method. The corresponding 95% confidence intervals for the median and quartiles will be constructed using the method of [Klein and Moeschberger \(1997\)](#) with log-log transformation. PFS rates at selected landmark time points will be provided and the corresponding 95% confidence intervals will be calculated using the method of [Kalbfleisch and Prentice \(1980\)](#). The duration of the follow-up for PFS will be estimated by reverse Kaplan-Meier method ([Schemper and Smith 1996](#)).

The inferential comparison between treatment groups will use the log-rank test stratified by the randomization stratification factors per IXRS at level of 0.025 (1-sided). The HR

and its 95% CI will be estimated using a Cox proportional hazards model stratified by the same randomization stratification factors.

The primary endpoint of PFS will be analyzed within each of the subgroups listed in [section 4](#). Specifically, to determine whether the treatment effect is consistent across subgroups, the estimate of the hazard ratios (with 95% CI) for PFS between the treatment groups will be provided. Additionally, a treatment-by-subgroup interaction test **may** be provided using a Cox proportional hazards model stratified by the stratification factors.

Piecewise Cox models may be explored given evidence of non-proportional hazards (Collett, 2003). This model will allow estimation of an overall weighted hazard ratio (weights equal to fraction of total events in each interval (Lu & Pajak, 2000)) as well as within interval treatment hazard ratio. Additional analysis may be performed to explore potential sources for non-proportionality by considering baseline prognostic factors and other potential confounding factors.

9.5.2 Analyses of Secondary Efficacy Endpoint(s)

Key secondary endpoints

If PFS is significant, the key secondary endpoints will be tested by sequential testing in the order of ORR, MRD[-]CR rate by NGS, and OS.

The analysis for ORR will be done if the primary analysis of PFS reaches statistical significance. **Subsequently, the analysis of MRD[-]CR rate will be done if ORR analysis reaches statistical significance.**

The inferential comparison between treatment groups for both the ORR and MRD[-]CR will be made using the Cochran Mantel Haenszel chi-square test controlling for the randomization stratification factors per IxRS. The ORR/MRD[-]CR will be calculated by treatment group and the associated 95% CI will be estimated using the Clopper-Pearson method. An estimate of the common odds ratio (95% CI) will be provided as a measure of the relative treatment effect. The odds ratio (and 95% CI) will be estimated using the Mantel-Haenszel method. The Kd arm will serve as the reference treatment group in the calculation of the odds ratio. The primary analysis of ORR will be based on IRC assessed outcomes. The analyses based on investigator-assessed and ORCA will serve as supportive analyses. Similarly, the CR portion of the MRD[-]CR endpoint will be based on IRC assessments. **The MRD assessment at month 12 is required for all subjects regardless of response. The subjects, who have progressed, might have**

withdrawn consent or stopped the study for other reasons prior to this time point, will be assessed as MRD positive and the reasons for not having an assessment will be summarized.

For subgroups listed in [section 4](#), odds ratio (with 95% CI) will be provided for ORR and MRD[-]CR rate between the treatment groups. A treatment-by-subgroup interaction test **may** be provided using a logistic regression model stratified by the stratification factors.

Overall survival will be analyzed using the same method as described for the PFS endpoints after PFS, ORR, MRD[-]CR all reach statistical significance. In the case that the PFS results are not statistically significant at the primary PFS analysis, the sponsor may stop the study and if so, the subjects will not be followed for OS any further.

Subgroup analysis for OS will be performed using the same method described for PFS as appropriate. If there is evidence to support non-proportional hazards, a piecewise proportional hazard model may be explored as described for PFS.

Other secondary endpoints

Duration of response (DOR) is defined as the time (in months) from first evidence of PR or better per IMWG-URC to the earlier of disease progression or death due to any cause for subjects with a best response of PR or better. For those who are alive and have not experienced disease progression at the time of data cutoff for analysis, duration of response will be right-censored based on the censoring conventions defined previously for PFS (refer to [Table 1](#)). The distribution of DOR, including the median and quartiles and their corresponding 95% CIs, will be characterized using the Kaplan-Meier method based on the subjects who achieve a best response of PR or better. No inferential comparison between treatment arms will be made for duration of response.

Time to next treatment is defined as the time (in months) from randomization to the initiation of subsequent non-protocol anti-cancer treatment for multiple myeloma. Time to next treatment for subjects who do not start the subsequent treatment for multiple myeloma will be censored at the date when the subject's information is last available. Time to next treatment will be summarized descriptively using the Kaplan-Meier method. This analysis will be based on the ITT population.

Time to progression (TTP) is defined as the time (in months) from randomization to documented disease progression. Analysis of TTP will be the same as PFS (see Section 8.4.1.1) except that death will be treated as a censoring event for TTP and will use similar methods as those for the primary PFS analysis based on the ITT population.

For descriptive purposes, time to overall response (defined as the time [in months] from randomization to the earliest of sCR, CR, VGPR, or PR per IMWG-URC) will be summarized using the descriptive statistics for a continuous variable by treatment group for those who achieve a best response of sCR, CR, VGPR, or PR.

The rate of sustained MRD[-]CR (defined as the proportion of subjects that maintain MRD[-]CR for 12 months or more after achieving MRD[-]CR status), the CRR rate (defined as the proportion of best overall response of sCR or CR), and the MRD[-] rate at 12-month will be compared between treatment groups using the similar method for ORR/MRD[-]CR analysis.

The inferential analysis of the endpoint of QLQ-C30 Global Health Status/QOL scale is described in [section 9.7.2](#).

CCI

CCI

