7.3.13 Survival

All subjects will be followed by telephone contact or other method approximately every 12 weeks (\pm 2 weeks) after the last follow-up visit until the subject has withdrawn consent for further participation, is lost to follow-up, has died, [REDACTED] or the study is closed, whichever is earliest. Vital status must be obtained for all subjects within the limits of local law. This includes subjects who may have discontinued study visits with or without withdrawing consent and should include interrogation of public databases, if necessary. If deceased, the date and reported cause of death should be obtained.

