7.3.14 Subsequent Antimyeloma Therapies

All subjects will be followed by telephone contact or other method to collect subsequent antimyeloma therapies approximately every 12 weeks (\pm 2 weeks) after the last follow-up visit until the subject has withdrawn consent for further participation, is lost to follow-up, has died, [REDACTED] or the study is closed, whichever is earliest.

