8. WITHDRAWAL FROM TREATMENT, PROCEDURES, AND STUDY

8.1 Subjects' Decision to Withdraw

Subjects have the right to withdraw from the study at any time and for any reason without prejudice to their future medical care by the physician or at the institution.

Subjects (or a legally acceptable representative) can decline to continue receiving investigational product and/or other protocol-required therapies or procedures at any time during the study but continue participation in the study. If this occurs, the investigator is to discuss with the subject the appropriate processes for discontinuation from investigational product, device or other protocol-required therapies and must discuss with the subject the options for continuation of the Schedule of Assessments (Table 11) including different options of follow-up (eg, in person, by phone/mail, through family/friends, in correspondence/communication with other treating physicians, from the review of medical records) and collection of data, including endpoints, adverse events, as applicable. Subjects who have discontinued investigational product and/or protocol required therapies or procedures should not be automatically removed from the study. Whenever safe and feasible it is imperative that subjects remain on-study to ensure safety surveillance and/or collection of outcome data. The investigator must document the level of follow-up that is agreed to by the subject.

Withdrawal of consent for a study means that the subject does not wish to receive further protocol-required therapies or procedures, and the subject does not wish to or is unable to continue further study participation. Subject data up to withdrawal of consent will be included in the analysis of the study, and where permitted, publically available data can be included after withdrawal of consent. The investigator is to discuss with the subject appropriate procedures for withdrawal from the study.

8.2 Investigator or Sponsor Decision to Withdraw or Terminate Subjects' Participation Prior to Study Completion

The investigator and/or sponsor can decide to withdraw a subject(s) from investigational product, device, and/or other protocol-required therapies, protocol procedures, or the study as a whole at any time prior to study completion.

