12.4 Investigator Responsibilities for Data Collection

The investigator is responsible for complying with the requirements for all assessments and data collection (including subjects not receiving protocol-required therapies) as stipulated in the protocol for each subject in the study. For subjects who withdraw prior to completion of all protocol-required visits and are unable or unwilling to continue the Schedule of Assessments ([Table 11](#)), the investigator can search publically available records (where permitted) to ascertain survival status. This ensures that the data set(s) produced as an outcome of the study is/are as comprehensive as possible.

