It will be calculated as the planned cumulative dose of **daratumumab** in mg/kg divided by the planned number of weeks for the treatment per protocol based on the corresponding cycle and day of the last **daratumumab** infusion. Per protocol, one cycle is 28 days (4 weeks), so the planned number of treatment weeks will be calculated as $4 \times (c-1) + j$, where c is the cycle in which the last daratumumab infusion is given and j =1 if the last daratumumab infusion is given on day 1 or 2 within the last cycle, j=2 if the last infusion is given on day 8, j=3 if the last infusion is given on day 15, j=4 if the last infusion is given on day 22. The planned cumulative dose of **daratumumab** is the summation of planned **daratumumab** dose (mg/m²) per week as : [8x2, 16x1, 16x1, 16x1] in cycle 1; [16x1, 16x1, 16x1, 16x1] in cycle 2; [16x1, 0, 16x1, 0] in cycle 3-6; and [16x1, 0, 0, 0] in all other cycles.

Study Day 1

Study Day 1 is the first day that the protocol-specified investigational products are administered to the subject.

Time to Complete Response

Time to complete response will be calculated only for the subjects who achieve a best overall response of CR or better, ie, sCR or CR. It will be calculated in months from randomization date to the earliest date of response of CR or better is first achieved and subsequently confirmed:

$$\text{Time to Complete Response} = (\text{response start date} - \text{randomization date} + 1) / 30.4$$

Time to Next Treatment

Time to next treatment is defined as the time (in months) from randomization to the initiation of subsequent non-protocol anti-cancer treatment for multiple myeloma.

Time to Progression (TTP)

TTP is defined as the time (in months) from randomization to documented disease progression.

Time to Response

Time to response will be calculated only for subjects who achieve a best overall response of PR or better, ie, sCR, CR, VGPR, or PR. It will be calculated in months from randomization date to the earliest date a response of PR or better is first achieved and subsequently confirmed:

$$\text{Time to Response} = (\text{response start date} - \text{randomization date} + 1) / 30.4$$

Treatment-emergent Adverse Event

Treatment-emergent adverse events (TEAE) are events with an onset after the administration of the first dose of any **study treatment** and within **the end of study or 30 days of the last dose of any study treatment, whichever occurs earlier**.

6. Analysis Sets

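### The time-to-next-treatment censoring date is not tied to therapy status, so for withdrawn or lost subjects later traced for survival, unobserved time can count as treatment-free

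*SAP*

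**What the plan says.** **Endpoint.** SAP section 5 gives the event only: "Time to next treatment is defined as the time (in months) from randomization to the initiation of subsequent non-protocol anti-cancer treatment for multiple myeloma". It contains no censoring rule.

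**Censoring.** The rule is in SAP 9.5.2, under the other secondary endpoints. Subjects who "do not start the subsequent treatment for multiple myeloma will be censored at the date when the subject's information is last available". The same paragraph plans a descriptive Kaplan-Meier summary in the ITT population.

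**Therapy data.** Protocol 7.3.14 follows subjects by telephone or other means "to collect subsequent antimyeloma therapies approximately every 12 weeks", and does so "until the subject has withdrawn consent for further participation, is lost to follow-up, has died", or the study closes.

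**Vital status.** Protocol 7.3.13 has the same 12-week contact and the same routine stopping conditions, and then goes further: "Vital status must be obtained for all subjects within the limits of local law". It adds: "This includes subjects who may have discontinued study visits with or without withdrawing consent and should include interrogation of public databases, if necessary". Two other sections support this. Under 8.1, "where permitted, publically available data can be included after withdrawal of consent". Under 12.4, for subjects who withdraw early and will not continue the schedule, "the investigator can search publically available records (where permitted) to ascertain survival status".

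**The concern.** A time-to-event endpoint should be censored when its own status was last known. For TTNT that is the last date on which somebody established that no new antimyeloma therapy had begun. A later record showing only that the subject is alive says nothing about therapy.

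If such a record sets the censoring date, the subject stays in the risk set through a period in which a next treatment could have started without being recorded. Missed events then count as event-free time, and the Kaplan-Meier curve is too high.

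The medians and landmark rates are at stake. The TTNT paragraph plans no test, so those estimates are the result. If such losses differed between the arms of this open-label trial, the contrast could also shift, in either direction.

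**Working it through.** **1. Do the two kinds of data end at different times?**

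| Subject's situation | Therapy status | Vital status |
|---|---|---|
| On treatment, or off treatment with 28-day disease assessments | seen at visits | seen at visits |
| Routine long-term follow-up | 12-weekly call (7.2.5, 7.3.14) | same call (7.2.5, 7.3.13) |
| Consent withdrawn or lost to follow-up | collection ends (7.3.14) | still sought where law permits, including public records (7.3.13, 8.1, 12.4) |

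Only the last row has a gap.

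**2. Does anything in the SAP close it?** Section 5 does not. Other endpoints have a specific date. Table 1 censors PFS for lost or withdrawn subjects at the last disease assessment. DOR uses Table 1, and TTP follows the PFS analysis. OS is censored at the date last known alive, capped at the analysis trigger date. The TTNT rule names neither a type of information nor a cap.

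**3. How large could the effect be?** The plan states no figure to reproduce. Every input below is an assumption unless a source is given.

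*Set A, closed form.*
- TTNT is exponential with a Kd median of 20 months, so λ = ln 2 / 20 = 0.03466 per month.
- A fraction p loses therapy ascertainment at a time uniform on 0 to 18 months, and all of them have vital status to cutoff.
- Follow-up is uniform on 16 to 27 months.

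A lost subject's event is seen only if it precedes the loss:

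q = 1 − (1 − e^(−18λ)) / (18λ) = 1 − (1 − 0.5359) / 0.6238 = 0.256

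For t ≥ 18, the literal rule estimates

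F*(t) = (1 − p)(1 − e^(−λt)) + p·q

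The true 18-month next-treatment rate is 1 − 0.5359 = 46.4%.

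- **p = 10%:** F*(18) = 0.90 × 0.4641 + 0.10 × 0.256 = 44.3%. For the median, 1 − e^(−λt) = (0.5 − 0.0256) / 0.90 = 0.5271, so t = 21.6 months, a shift of 1.6.
- **p = 5%:** 1 − e^(−λt) = (0.5 − 0.0128) / 0.95 = 0.5128, so t = 20.75 months, a shift of about 0.8.

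*Set B, simulation with 400,000 subjects per arm.* Protocol figures serve as proxies:
- Kd median 18.7 months (the PFS median in 2.5.4);
- HR 0.6 (10.2), so the KdD median is 18.7 / 0.6 = 31.2 months;
- survival after loss with median 47.6 months (the OS median in 2.5.4);
- accrual over 11 months (3.5.1).

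Assumed: 48 to 59 months of follow-up per subject, exponential loss of therapy data reaching the stated percentage by month 24, and half to all of those lost traced later.

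| Lost by month 24 | Kd median (true 18.7) | KdD median (true 31.2) |
|---|---|---|
| 5% | 18.9 to 19.1 | 31.7 to 32.4 |
| 10% | 19.1 to 19.6 | 32.5 to 33.9 |

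In set B the Kd shift is 0.2 to 0.4 months at 5% and 0.4 to 0.9 at 10%. It is smaller than in set A because fewer losses fall before the median (at 10%, 1 − 0.9^(18.7/24) = 7.9%), and because tracing is partial or ends at death.

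In both sets, censoring at the last known therapy status recovers the true medians, because loss was assumed independent of the event.

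**4. Unequal losses.** On set A inputs with HR 0.60, losing 15% in Kd and 5% in KdD moves the rate ratio to about 0.64; the reverse moves it to 0.56. Nothing in the documents indicates which pattern, if any, would occur.

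**The case against.** **The SAP never says information of any kind.** This is true. The SAP defines a last known alive date, which includes survival-form contacts, and the TTNT rule does not cite it. A sensible programmer might take the phrase to mean information about therapy. But the phrase is unqualified and nothing narrows it, so the literal reading is open and it is the one that biases the curve. What stands is that a reader may not infer that survival-only dates will certainly be used.

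**The gap is small.** This also largely stands. The routine stopping conditions in 7.3.13 and 7.3.14 are the same, and 7.2.5 puts both items on one call. For subjects who stop treatment or visits without withdrawing consent, 8.1 offers follow-up through treating physicians and medical records. What remains is subjects who withdrew fully or were lost, and were later traced for survival alone.

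**Two stronger readings should be resisted.**
- *Amendment 4.* The log says that therapy collection in long-term follow-up was added then, so a reader might infer that earlier survival contacts carry no therapy data. The documents do not support this. Therapy records carry start dates, SAP Appendix A imputes partial ones, and a later contact can record a therapy begun earlier. The SAP is written to Amendment 4 and already includes this collection.
- *A biased arm comparison.* A reader might infer that the contrast is distorted in a known direction. The documents give no withdrawal rates by arm, and the TTNT paragraph plans no hazard or rate ratio, although protocol 1.2 lists TTNT among the comparisons between arms.

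**Conclusion.** The point holds as a defect in a stated rule, limited to subjects whose therapy follow-up ended through withdrawal or loss and whose vital status was found later. For them the literal rule counts unobserved time as treatment-free. The upward direction follows from the rule itself; the size does not.

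On assumed losses of 5% to 10% per arm with later vital status known for half or more, the Kd median rises by roughly 0.2 to 1.6 months across the two sets of assumptions. With few such subjects the effect is negligible. Distortion between arms is only a possibility, in either direction.

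TTNT is an additional secondary endpoint outside the testing hierarchy, so type I error and the conclusions on PFS, ORR, MRD[-]CR and OS are unaffected.

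One limit on the reading: the protocol text is Amendment 6, while the SAP refers to Amendment 4, whose wording of 7.3.13 is not available here.

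**What to change.** In SAP 9.5.2, replace the TTNT censoring date with the last date on which the subject was known not to have started subsequent antimyeloma therapy. List the sources: the last on-treatment visit, an off-treatment disease-assessment visit, follow-up visit 1, or a long-term follow-up contact with therapy status recorded. Take the latest of these, no later than the data cutoff. Then add two statements:

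- records giving vital status only do not extend TTNT follow-up;
- how death before any next treatment is handled, which the paragraph leaves open.

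This matches the principle that Table 1 already applies to PFS. The cost is a few lines of SAP text and one re-derived date. Some subjects will have slightly shorter TTNT follow-up.
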